## 10.3 Cycle 2 and all subsequent cycles

Patients will return to the clinic and undergo the following procedures:

- AE monitoring
- Recording of concomitant medications

- Vital signs and weight
- Symptom-directed physical exam
- Clinical laboratory values (hematology, coagulation, serum chemistry and urinalysis)
- ECOG performance status evaluation
- Plasma sample for collection for biomarker analysis taken prior to dosing on Cycles 2 and 3 Day 1
- Whole blood sample collection for biomarker analysis taken prior to dosing on Cycles 2 and 3 Day 1
- Administration of CB-839 and nivolumab
  - Patients should be instructed not to eat breakfast prior to their clinic visit on Cycle 2 Day 1 and Cycle 3 Day 1. Patients will undergo the predose assessments prior to receiving the nivolumab infusion or eating breakfast and receiving the CB-839 dose. The 2nd dose of CB-839 will be self-administered by the patient per dosing instructions after all study procedures have been completed.
- A postdose tumor biopsy will be obtained from all patients in Phase 1 backfill cohorts, Phase 2- Cohorts 2, 4, and 5 on Cycle 2 Day 1 only ( $\pm$  1 week). Coagulation tests must be performed and evaluated within 72 to 24 hr prior to all biopsy procedures.
- Radiographic evaluation (e.g., diagnostic CT or MRI) of tumor burden will occur approximately every 8 weeks. The same method of evaluation should be used throughout the course of the study. The scans and redacted reports will be collected and sent to a central reader for exploratory evaluation.

#### 10.4 Other Schedules and Procedures

Radiographic evaluation of tumor burden (e.g., diagnostic CT/MRI) will occur at Screening and approximately every 8 weeks from Cycle 1 Day 1 and as clinically indicated.

Optional tumor biopsies may be obtained at variable time points as advised by the Investigator.

### 10.5 End of Treatment (EOT)

The End of Treatment (EOT) visit must occur within 28 days of treatment discontinuation and prior to initiation of any new anti-cancer therapy/regimen. All patients discontinuing study treatment for any reason should undergo the following EOT procedures:

- AE monitoring
- Recording of concomitant medications
- Vital signs and weight
- Complete physical examination
- ECOG performance status evaluation
- Clinical laboratory values (hematology, coagulation, serum chemistry and urinalysis)
- Urine pregnancy test for women of child-bearing potential
- 12-lead ECG with QTcF
- Radiographic evaluation (e.g., diagnostic CT or MRI) of tumor burden. Patients who discontinue from study due to objective findings of progressive disease during an on-treatment evaluation do not need to have repeat scans. CT or MRI is required for all patients who have not had at least 1 post-baseline image.

### 10.6 Follow Up

Patients who discontinue study treatment for reason other than PD or death must continue to be followed by radiographic imaging per study schedule until PD, death, withdrawal of consent or initiation of another cancer therapy. All patients who discontinue study treatment will be contacted every 3 mo for the first 12 mo and then once every 6 mo thereafter for survival follow-up. All reasonable efforts must be made to contact patients and report their ongoing status. This includes follow up with persons authorized by the patient. If the patient or authorized persons cannot be contacted, public records may be consulted to establish survival status.

### 10.7 Screen Failures

Patients who sign an informed consent form, are not assigned to a treatment, and do not receive either CB-839 or nivolumab are defined as screen failures. For all screen failures, the Investigator will enter the screening number, patient initials, and reason(s) for screen failure into

the electronic data capture (EDC) system. These data will also be retained in the Investigator's study files and can be printed by the site in log format at the end of the study.

## 10.8 Dose Modification and Management of Toxicities

### 10.8.1 Potential Toxicities

#### 10.8.1.1 CB-839

As of 8 Oct 2015, CB-839 had been administered as a single agent to 98 patients with advanced/metastatic solid tumors on the Phase 1 CX-839-001 protocol. During this study, CB-839 was dosed either three times daily (TID; 100-1000 mg) without food or twice daily (BID; 600-1000 mg) with meals. Due to differences in the pharmacokinetic and safety profiles between the two regimens (including reduced Grade 3/4 liver function test (LFT) elevations; data are reported by regimen below), patients enrolled on the current study will receive CB-839 in the "BID with meals" regimen.

The most frequent adverse events (AEs) considered possibly or probably related to CB-839 monotherapy on the CX-839-001 were fatigue, nausea, LFT elevations and photophobia ([Table 10.7-1](#)). These have been primarily Grade 1/2 AEs that have been manageable and reversible with minimal dose modifications or delays.

**Table 10.7-1: Drug-related AEs reported in  $\geq 2$  subjects on study CX-839-001**

All AE Grades	Number (%) of patients		
	All (N=98)	TID (N=32)	BID (N=66)
MedDRA Preferred Term			
Patients with any AE	67 (68.4)	23 (71.9)	44 (66.7)
FATIGUE	24 (24.5)	8 (25.0)	16 (24.2)
ALANINE AMINOTRANSFERASE INCREASED	14 (14.3)	6 (18.8)	8 (12.1)
NAUSEA	14 (14.3)	2 (6.3)	12 (18.2)
ASPARTATE AMINOTRANSFERASE INCREASED	13 (13.3)	6 (18.8)	7 (10.6)
PHOTOPHOBIA	8 (8.2)	1 (3.1)	7 (10.6)
GAMMA-GLUTAMYLTRANSFERASE INCREASED	7 (7.1)	1 (3.1)	6 (9.1)
VOMITING	7 (7.1)	4 (12.5)	3 (4.5)
BLOOD ALKALINE PHOSPHATASE INCREASED	5 (5.1)	2 (6.3)	3 (4.5)
DECREASED APPETITE	5 (5.1)	--	5 (7.6)
BLOOD CREATININE INCREASED	4 (4.1)	1 (3.1)	3 (4.5)
CONSTIPATION	3 (3.1)	2 (6.3)	1 (1.5)

DYSPEPSIA	3 (3.1)	--	3 (4.5)
PHOTOSENSITIVITY REACTION	3 (3.1)	--	3 (4.5)

The most frequent Grade 3/4 AEs considered possibly or probably related to monotherapy CB-839 were LFT elevation (Table 10.7-2). The rate of Grade 3/4 LFT elevations was notably lower when CB-839 was dosed BID with meals as compared to the TID dosing regimen. When LFT elevations occurred, they were generally rapidly reversible and manageable with dose reduction.

**Table 10.7-2: Drug-related  $\geq$  Grade 3 AEs reported on study CX-839-001**

$\geq$ Grade 3 AEs	Number (%) of patients		
	All (N=98)	TID (N=32)	BID (N=66)
MedDRA Preferred Term			
Patients with any AE	10 (10.2)	7 (21.9)	3 (4.5)
ALANINE AMINOTRANSFERASE INCREASED	6 (6.1)	5 (15.6)	1 (1.5)
ASPARTATE AMINOTRANSFERASE INCREASED	5 (5.1)	5 (15.6)	0
GAMMA-GLUTAMYLTRANSFERASE INCREASED	3 (3.1)	1 (3.1)	2 (3.0)
BLOOD ALKALINE PHOSPHATASE INCREASED	1 (1.0)	1 (3.1)	0
BLOOD CREATININE INCREASED	1 (1.0)	1 (3.1)	0
HYPOGLYCAEMIA	1 (1.0)	1 (3.1)	0

### 10.8.1.2 Nivolumab

Nivolumab (OPDIVO®) is an anti-PD-1 monoclonal antibody that has been FDA approved for the treatment of certain patients with unresectable or metastatic melanoma, metastatic NSCLC, and advanced RCC. The safety profile of nivolumab is fully described in the [nivolumab package insert](#) and primarily consists of immune-related adverse events (ir-AEs) due to activation and proliferation of T-cells. Ir-AEs can affect any organ or tissue but most frequently occur in the skin (rash), gastrointestinal system (diarrhea/colitis), liver (hepatitis), lungs (pneumonitis), endocrine system (endocrinopathies due to inflammation of the pituitary, thyroid and adrenals), and kidneys (nephritis). The management of these toxicities is described in the package insert but generally includes holding drug for moderate (Grade 2) toxicities and using systemic immunosuppression for severe (Grade 3/4) or prolonged moderate ( $>$  1 week) toxicities. Additional immunosuppression (e.g., anti-TNF $\alpha$  therapy, infliximab) may be used if IV steroids are ineffective.

### 10.8.1.3 CB-839 and Nivolumab Combination

The tolerability of CB-839 in combination with nivolumab is not known. A primary objective of the current study is to evaluate the safety and tolerability of the combination of nivolumab and CB-839. There are no clinical data evaluating the combination of these two agents. Preclinical studies of the combination of an anti-PD-1 agent and CB-839 have been performed in mice for the purpose of evaluating the anti-tumor activity of the combination. In these experiments, the combination of anti-PD-1 and CB-839 appeared to be well tolerated but an extensive safety evaluation was not performed.

### 10.8.2 Dose Modifications and Toxicity Management

The safety and tolerability profile of CB-839 is summarized above ([Section 10.8.1.1](#)). In general, management of AEs related to CB-839 includes withholding the medication for moderate to severe toxicities and providing the appropriate supportive care.

The safety and tolerability profile of nivolumab is well defined and outlined in the [nivolumab package insert](#). Ir-AEs are defined in the nivolumab label as those that occur while receiving nivolumab, require immunosuppression and have no clear alternate etiology. Guidelines for the management of ir-AEs and study drug dosing are provided below for reference but Investigators are encouraged to follow the most current product label for nivolumab. In general, for moderate to severe ir-AEs, nivolumab should be withheld or permanently discontinued and, depending on the nature of the AE, it should be managed with high-dose corticosteroids and hormone-replacement therapy, if necessary. Upon improvement to Grade 1 or less, a corticosteroid taper should be initiated and continued over at least 1 mo. Restarting nivolumab may be considered after completion of corticosteroid taper based on the severity of the event. In some cases, the natural history of AEs associated with immunotherapy can differ from and be more severe than AEs caused by agents belonging to other therapeutic classes. Early recognition and management may mitigate severe toxicity. Evaluation and management guidelines for the following types of ir-AEs are provided in the [nivolumab package insert](#): pneumonitis, colitis, hepatitis, endocrinopathies, nephritis/renal dysfunction, rash, and encephalitis.

For patients in the Dose Escalation Phase, dose reductions of CB-839 will be permitted during Cycle 1 (first 28 days) *only if a patient experiences DLT or a toxicity that may herald a DLT*. If

a patient experiences a DLT, treatment continuation at a lower dose of CB-839 will be permitted as long as the toxicity has returned to  $\leq$  Grade 1 or baseline within 28 days and nivolumab therapy can be continued. Upon recovery, patients may restart at one CB-839 dose level lower. Patients who do not recover within 28 days will not be eligible for resumption of study treatment. After Cycle 1, dose reductions or interruptions for adverse events may take place at any time at the discretion of the Principal Investigator in consultation with the Medical Monitor.

### 10.8.2.1 Dose Modification Guidelines

Patients will be monitored continuously for AEs while on study. Treatment modifications (e.g., dose delay) will be based on specific laboratory and AE criteria. Guidelines for dose modifications due to AEs are based on the nivolumab product label and the clinical experience with CB-839 to date and are provided in [Table 10.8-1](#). Study drugs may be held and restarted independently depending upon the adverse event. Because product labels may change over time, when in doubt investigators should always refer to the most current nivolumab product label. The study guidelines are intended primarily for toxicities that are not easily managed with routine supportive care. For example, alopecia does not require dose modification nor does Grade 2 nausea/vomiting that are easily managed with anti-emetics. Importantly, these guidelines are not meant to replace the clinical judgment of the Investigator caring for the patient or the most recent nivolumab product label and should be used as guidelines. Additional information regarding the management of specific toxicities is provided in [Table 10.8-1](#).

*These parameters are only guidelines and are not intended to supersede the clinical judgment of the treating physician.* Investigators should err on the side of caution in the setting of potential ir-AEs. Investigators should contact the Medical Monitor if 1) a dose modification is planned, 2) systemic immunosuppression is required (however, if immediate systemic immunosuppression is required, please DO NOT delay the start of immunosuppressive therapy in order to speak with the Medical Monitor), or 3) there is a preference to deviate from the guidelines for the management of AEs or dose modifications. Holding of the study drug and study discontinuation for both non-hematological and hematological toxicities will be based on the Principal Investigator's judgment following discussion with the Medical Monitor.

### 10.8.2.2 Resumption of Study Treatment

For both CB-839 and nivolumab, treatment may be delayed for up to 4 weeks from the last dose before restarting. CB-839 and nivolumab may be held and restarted independent of each other. Treatment delays longer than 4 weeks are allowed only in cases where a prolonged steroid taper is required to manage drug-related AEs or, in some cases, if the delay was due to a non-drug related cause. Prior to re-initiating treatment in a patient with a dosing interruption lasting > 4 weeks, the Medical Monitor must be consulted. Treatment compliance will be monitored by drug accountability as well as the patient's medical record and eCRF.

Upon withholding study drug(s) for adverse events, the study drug(s) may be restarted when the AE has returned to  $\leq$  Grade 1. For patients that require a steroid taper, nivolumab should not be restarted until the steroid taper is complete. In cases in which a particular toxicity is clearly related to only one of the two study drugs, the study drug that is not involved in causing the AE may be continued or restarted prior to AE resolution to  $\leq$  Grade 1 or baseline. If CB-839 is restarted after permanent discontinuation of nivolumab, CB-839 should also be permanently discontinued for a  $\geq$  Grade 3 recurrence of the AE that resulted in nivolumab discontinuation.

**Table 10.8-1: Dose Modification Guidelines for irAEs**

Adverse Reaction	Severity	Management	Dose Modification
Colitis	Grade 2	If >5 days, 0.5 to 1 mg/kg/day prednisone. If worsening or no improvement, increase to 1 to 2 mg/kg/day prednisone equiv. and consider IV.	Nivo: Withhold dose CB: Withhold dose
	Grade 3	1 to 2 mg/kg/day prednisone equiv. Consider IV.	Nivo: Withhold dose CB: Withhold dose
	Grade 4	1 to 2 mg/kg/day prednisone equiv. Consider IV.	Nivo: Permanently discontinue CB: Withhold dose. Consider re-challenge with monotherapy.
Pneumonitis	Grade 2	1 to 2 mg/kg/day prednisone equiv.	Nivo: Withhold dose CB: Withhold dose
	Grade 3 or 4	1 to 2 mg/kg/day prednisone equiv. Consider IV.	Nivo: Permanently discontinue CB: Withhold dose. Consider re-challenge with monotherapy.
Hepatitis	AST or ALT > 3 to 5x ULN or total bilirubin > 1.5 to 3x ULN	Monitor closely. If continues $\geq$ 1 week, 1 to 2 mg/kg/day prednisone equiv.	Nivo: Withhold dose CB: Withhold dose
	AST or ALT > 5x ULN or total bilirubin > 3x ULN	1 to 2 mg/kg/day prednisone equiv. Consider IV.	Nivo: Permanently discontinue CB: Withhold dose. Consider re-challenge with monotherapy.
Hypophysitis	Grade 2 or 3 hypophysitis	1 mg/kg/day prednisone equiv.	Nivo: Withhold dose CB: Withhold dose
	Grade 4 hypophysitis	1 mg/kg/day prednisone equiv.	Nivo: Permanently discontinue CB: Withhold dose. Consider re-challenge with monotherapy.
Adrenal Insufficiency	Grade 2 adrenal insufficiency	None	Nivo: Withhold dose CB: Withhold dose
	Grade 3 or 4 adrenal insufficiency	1 to 2 mg/kg/day prednisone equiv. Consider IV.	Nivo: Permanently discontinue CB: Withhold dose. Consider re-challenge with monotherapy.
Type 1 Diabetes Mellitus	Grade 3 hyperglycemia	Manage glucose with insulin	Withhold both drugs. Restart upon glucose control.
	Grade 4 hyperglycemia	Manage glucose with insulin	Nivo: Permanently discontinue CB: Withhold dose. Consider re-challenge with monotherapy.

Adverse Reaction	Severity	Management	Dose Modification
Nephritis and Renal Dysfunction	Serum creatinine > 1.5x to 6x ULN	0.5 to 1 mg/kg/day prednisone. If worsening or no improvement, increase to 1 to 2 mg/kg/day prednisone equiv. and consider IV.	Nivo: Withhold dose CB: Withhold dose
	Serum creatinine > 6x ULN	1 to 2 mg/kg/day prednisone equiv. Consider IV.	Nivo: Permanently discontinue CB: Withhold dose. Consider re-challenge with monotherapy.
Skin	Grade 3 rash or suspected Stevens-Johnson syndrome (SJS) or toxic epidermal necrolysis (TEN)	1 to 2 mg/kg/day prednisone equiv. Consider IV.	Nivo: Withhold dose CB: Withhold dose
	Grade 4 rash or confirmed SJS or TEN	1 to 2 mg/kg/day prednisone equiv. Consider IV.	Nivo: Permanently discontinue CB: Withhold dose. Consider re-challenge with monotherapy.
Infusion Reaction	Grade 1	Manage per product label and institutional standard for infusion reactions. For subsequent nivolumab doses, premedicate with diphenhydramine and acetaminophen.	Nivo: No change
	Grade 2	Manage per product label and institutional standard for infusion reactions. For subsequent nivolumab doses, premedicate with diphenhydramine and acetaminophen.	Nivo: Hold dose until resolution of symptoms. Restart at 50% of the original infusion rate. If no symptoms for 30 minutes, consider returning to 100% of the original infusion rate.
	Grade 3 or 4	Manage per product label and institutional standard for infusion reactions	Nivo: Permanently discontinue
Encephalitis	New-onset moderate or severe neurologic signs or symptoms	Evaluate to rule out other causes (infectious, other). Evaluation may include, but not be limited to, consultation with a neurologist, brain MRI, and lumbar puncture. If other causes are ruled out, start 1 to 2 mg/kg/day prednisone equiv. Consider IV.	Nivo: Withhold dose CB: Withhold dose
	Immune-mediated encephalitis	1 to 2 mg/kg/day prednisone equiv. Consider IV.	Nivo: Permanently discontinue CB: Withhold dose. Consider re-challenge with monotherapy.

Adverse Reaction	Severity	Management	Dose Modification
Other irAE	Other Grade 3 adverse reaction (with the exception of fatigue or clinically irrelevant laboratory values)		
	
 
First occurrence
 
	1 to 2 mg/kg/day prednisone equiv. Consider IV.	Nivo: Withhold dose CB: Withhold dose
	
 
Recurrence of same Grade 3 adverse reaction
 
	1 to 2 mg/kg/day prednisone equiv. Consider IV.	Nivo: Permanently discontinue CB: Withhold dose. Consider re-challenge with monotherapy.
	Life-threatening or Grade 4 adverse reaction	1 to 2 mg/kg/day prednisone equiv. Consider IV.	Nivo: Permanently discontinue CB: Withhold dose. Consider re-challenge with monotherapy.
	Requirement for 10 mg per day or greater prednisone or equivalent for more than 12 weeks		Nivo: Permanently discontinue CB: Consider re-challenge/continuation with CB-839 monotherapy.
	Persistent Grade 2 or 3 adverse reactions lasting 12 weeks or longer		Nivo: Permanently discontinue CB: Permanently discontinue

### 10.8.2.3 Supportive Care Guidelines

Patients should receive appropriate supportive care measures as deemed necessary by the treating Investigator. Guidelines outlined below should be used in conjunction with information provided in the nivolumab product label:

**Diarrhea:** Patients should be monitored for signs and symptoms of enterocolitis (such as diarrhea, abdominal pain, blood or mucus in stool, with or without fever) and of bowel perforation (such as peritoneal signs and ileus). In symptomatic patients, infectious etiologies should be ruled out, and if symptoms are persistent and/or severe, endoscopic evaluation should be considered. In patients with severe enterocolitis, nivolumab will be permanently discontinued and treatment with systemic corticosteroids should be initiated at a dose of 1 to 2 mg/kg/day of prednisone or equivalent. In patients that do not respond to high dose steroids with 72 hr, consider initiation of additional immunosuppressive therapy (e.g., infliximab). When symptoms improve to Grade 1 or less, corticosteroid taper should be started and continued over at least 1 mo.

In patients with moderate enterocolitis, nivolumab should be withheld and antidiarrheal treatment should be started. If symptoms are persistent for more than one week, systemic corticosteroids should be initiated (e.g., 0.5 mg/kg/day of prednisone or equivalent). When

symptoms improve to Grade 1 or less, corticosteroid taper should be started and continued over at least 1 mo. Regarding guidelines for continuing treatment with CB-839 and nivolumab, see [Table 10.8-1](#).

All patients who experience diarrhea should be advised to drink liberal quantities of clear fluids. If sufficient oral fluid intake is not feasible, fluid and electrolytes should be substituted via IV infusion.

**Nausea/vomiting:** Nausea and vomiting should be treated aggressively, and consideration should be given in subsequent cycles to the administration of prophylactic antiemetic therapy according to standard institutional practice. Patients should be strongly encouraged to maintain liberal oral fluid intake.

**Anemia:** Transfusions and/or erythropoietin may be utilized as clinically indicated for the treatment of anemia, but should be clearly noted as concurrent medications.

**Neutropenia:** Prophylactic use of colony-stimulating factors including Granulocyte Colony-Stimulating Factor (G-CSF), pegylated G-CSF or Granulocyte Macrophage Colony-Stimulating Factor GM-CSF is not allowed in this study. Therapeutic use of G-CSF is allowed in patients with Grade 3-4 febrile neutropenia.

**Thrombocytopenia:** Transfusion of platelets may be used if clinically indicated. ITP should be ruled out before initiation of platelet transfusion.

**Anti-infectives:** Patients with a documented infectious complication should receive oral or IV antibiotics or other anti-infective agents as considered appropriate by the treating Investigator for a given infectious condition, according to standard institutional practice.

**Immune-related adverse events:** Patients who develop a Grade 2 or higher irAE (e.g., colitis, skin rash, hepatitis, uveitis, hypo- or hyperthyroidism, hypophysitis, or any other), should be discussed immediately with the Medical Monitor. Depending on the type and severity of an irAE, oral or intravenous treatment with a corticosteroid should be considered, in addition to appropriate symptomatic treatment of a given condition. For severe immune-mediated adverse events that do not respond to high dose IV steroids within 72 hr, consider initiation of additional immunosuppressive therapy (e.g., infliximab for non-hepatic toxicities or mycophenolate mofetil for immune-mediated hepatotoxicity).

**Infusion reaction:** Infusion reactions may consist of fever, chills/rigor, nausea, pruritus, angioedema, hypotension, headache, bronchospasm, urticaria, rash, vomiting, myalgia, dizziness or hypertension. Severe reactions may include acute respiratory distress syndrome, myocardial infarction, ventricular fibrillation, and cardiogenic shock. Patients should be closely monitored for an infusion reaction during and immediately following drug infusion.

In the event of a Grade 2 infusion reaction, interrupt the infusion until the symptoms resolve and then restart at a reduced infusion rate (50% of original rate). If the symptoms do not return after 30 minutes at the reduced infusion rate, consider returning to the original infusion rate. Proper medical management should be instituted, as indicated per type of the reaction. This includes but is not limited to an antihistamine (e.g., diphenhydramine or equivalent), anti-pyretic (e.g., paracetamol or equivalent), and if considered indicated oral or IV glucocorticoids, epinephrine, bronchodilators, and oxygen.

In the event of a Grade 3 or 4 infusion reaction, immediately stop the infusion. Proper medical management should be instituted immediately, as indicated per type and severity of the reaction. This may include but is not limited to oral or IV anti-histamine, anti-pyretic, glucocorticoids, epinephrine, bronchodilators, and oxygen.

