### **7.5.2 Adverse Events**

Verbatim description of adverse events will be coded to System Organ Class (SOC) and Preferred Term (PT) using the Medical Dictionary for Regulatory Activities (MedDRA) and graded by the investigator according to NCI CTCAE v4.03. Treatment-emergent AEs (TEAEs) are defined as AEs started or worsened on or after first dose and will be tabulated. The number and proportion of patients reporting a given TEAE will be tabulated according to the worst severity grade reported. Separate tables will be constructed for a) all reported TEAE's, b) serious TEAEs (treatment-emergent SAEs), c) severe TEAEs (Grade  $\geq 3$ ), and d) TEAE's leading to permanent discontinuation or interruption of study treatments. The above tables will also be presented for TEAEs judged to be related to either study treatment.

Multiple occurrences of the same event will be counted once at the maximum grade. In order to accurately summarize the true TEAE rate, all TEAE summaries will not count grade 5 events for patients who died due to progressive disease.

All listings of adverse events will include both TEAEs and non-TEAEs.

Deaths reported during the study treatment period and the follow-up period after treatment completion/discontinuation will be listed and summarized by cause.

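### After a first Grade 3 colitis, Section 10.8.2.3 stops nivolumab permanently while Table 10.8-1 only withholds it

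*Protocol*

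**What the plan says.** Three parts of the protocol bear on nivolumab dosing after colitis.

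- **Section 10.8.2.3, Diarrhea paragraphs.** There are two tiers, neither tied to a grade. For the upper tier: "In patients with severe enterocolitis, nivolumab will be permanently discontinued and treatment with systemic corticosteroids should be initiated". For the lower tier: "In patients with moderate enterocolitis, nivolumab should be withheld and antidiarrheal treatment should be started". In the lower tier, steroids follow if symptoms last more than one week. The lower-tier paragraph ends by sending the reader to Table 10.8-1 for guidance on continuing treatment.
- **Table 10.8-1, Colitis rows.** There are three tiers by grade. Grades 2 and 3 carry the same dosing instruction: "Nivo: Withhold dose CB: Withhold dose". Grade 4 carries: "Nivo: Permanently discontinue CB: Withhold dose. Consider re-challenge with monotherapy". Grade 2 steroids start after more than 5 days; the Grade 3 row gives steroids with no waiting period.
- **Section 10.8.2.2.** A drug withheld for an adverse event may restart once the event is Grade 1 or less. Where a steroid taper was needed, nivolumab waits until the taper is complete.

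The link between words and grades is in Section 10.8.1.2, which describes nivolumab toxicity management as "holding drug for moderate (Grade 2) toxicities and using systemic immunosuppression for severe (Grade 3/4) or prolonged moderate" toxicities.

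**The concern.** Read with Section 10.8.1.2, a first Grade 3 colitis is *severe*, so Section 10.8.2.3 ends nivolumab for that patient. Table 10.8-1 treats the same event as a hold, after which Section 10.8.2.2 allows a restart. Two sites could handle the same event in opposite ways and each cite the protocol.

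Colitis is among the immune-related toxicities that Section 10.8.1.2 lists as most frequent, and Section 10.8.2.3 itself warns of bowel perforation. Section 10.8.1.3 says the tolerability of the combination is not known, and safety and tolerability are a primary objective. The rule decides whether a patient resumes the combination or loses nivolumab for good. In dose escalation it can also matter for CB-839, because Section 10.8.2 lets a patient continue at a lower CB-839 dose after a DLT only if nivolumab can be continued.

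**Working it through.** There is no figure to reproduce. The check sets the passages side by side.

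**Step 1: what *severe* covers.** Section 10.8.2.3 gives no grade. Section 10.8.1.2 uses the same pair of words for nivolumab toxicities, with moderate as Grade 2 and severe as Grade 3/4. SAP Section 7.5.2 also tabulates severe events as Grade 3 or higher, but that is a reporting category and adds little. The mapping rests mainly on Section 10.8.1.2.

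**Step 2: nivolumab instruction by grade.**

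| Colitis grade | Section 10.8.2.3 | Table 10.8-1 | Result |
|---|---|---|---|
| 2 (moderate) | Withhold | Withhold | Agree |
| 3 (severe) | Stop permanently | Withhold | Conflict |
| 4 (severe) | Stop permanently | Stop permanently | Agree |

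One grade of three is in conflict.

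**Step 3: whether the table route really permits re-exposure.** It does. Section 10.8.2.2 allows a restart at Grade 1 or less after the taper. The extra stopping rules at the end of the table (recurrent Grade 3 events, prolonged steroids, events lasting 12 weeks or longer) sit under other irAEs. They do not turn a first Grade 3 colitis into a permanent stop.

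**Step 4: the other reading.** Suppose *severe* meant Grade 4 only. Grade 3 is then either not covered by the text or counted as moderate. If moderate, nivolumab is withheld in both places and the dosing conflict disappears. Steroids would then wait more than one week under the text, against no wait in the table's Grade 3 row. That reading replaces one mismatch with a different one, and it contradicts Section 10.8.1.2.

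**Step 5: Grade 2 steroid trigger.** More than 5 days means day 6 at the earliest. More than one week (7 days) means day 8 at the earliest. The gap is 8 − 6 = 2 days, in steroid start only.

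**Step 6: whether a restart would be reviewed.** Sections 10.8.2 and 10.8.2.3 require a taper of at least 1 month, begun once the event has improved to Grade 1 or less. The last nivolumab dose comes before the taper. Taking a month as at least 28 days, a restart after steroid-treated Grade 3 colitis falls more than 4 weeks after the last dose, and Section 10.8.2.2 then requires Medical Monitor consultation.

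**The case against.** The best case on the other side is that the protocol already says where the dosing rule sits. Section 10.8.2.3 is headed as supportive care and refers to Table 10.8-1 for continuing treatment; Section 10.8.2.1 places the dose-modification guidance in the same table. The guidance is not binding. It yields to clinical judgment and to the current label, and it asks for caution. Section 10.8.2 allows either a hold or a permanent stop for moderate to severe events and makes restart optional. All of this stands and limits the consequences. It does not settle which rule applies, because no sentence says that the table overrides the unconditional stop in Section 10.8.2.3.

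Three stronger inferences are tempting, and the documents do not support them.

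- *The two instructions cannot both be obeyed.* They can: an investigator who holds nivolumab at Grade 3 and never restarts it satisfies both. Only an elective restart is forbidden by one passage and allowed by the other.
- *A restart could go unreviewed.* This is unlikely. Section 10.8.2.3 calls for immediate discussion of any irAE of Grade 2 or higher with the Medical Monitor, Section 10.8.2.1 asks for contact when a dose modification is planned, and consultation before restart follows from Step 6.
- *The steroid dose shows that severe means Grade 3.* The text's dose for severe disease, "at a dose of 1 to 2 mg/kg/day of prednisone or equivalent", does match the Grade 3 row, "1 to 2 mg/kg/day prednisone equiv. Consider IV", but the Grade 4 row is the same. The dose cannot separate the two grades.

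**Conclusion.** The inconsistency is real and confined to Grade 3: after a first Grade 3 colitis, the protocol both forbids and permits a nivolumab restart. The Grade 2 steroid mismatch is minor. The documents do not show which rule is right, so a reader should not infer that either the text or the table is the error; that depends on the current nivolumab label, which was not available for this review.

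The impact is limited by the pointer to the table, the deference to the label and Medical Monitor contact. The number of patients affected cannot be estimated, since no colitis incidence is given for the combination. A size in missed nivolumab doses would not be informative either, because the protocol sets no fixed number of cycles. Sample size, error rates and planned analyses are unaffected.

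The conclusion assumes that *severe* in Section 10.8.2.3 has its Section 10.8.1.2 meaning, and that enterocolitis in the text and colitis in the table are the same event. It should be corrected because it is a patient-safety instruction and the correction is cheap.

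**What to change.** 1. Check the Grade 3 colitis row of Table 10.8-1 against the current nivolumab label.
2. If the row stands, replace the severe/moderate wording in Section 10.8.2.3 with the table's rule: withhold nivolumab at Grades 2 and 3, stop it permanently at Grade 4. If the label requires discontinuation at Grade 3, change the table row instead and give Section 10.8.2.3 the matching grades.
3. State in Section 10.8.2.3 that Table 10.8-1 governs nivolumab dosing.
4. In the same edit, set the Grade 2 steroid trigger in Section 10.8.2.3 to more than 5 days, as in the table.

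The cost is one label check and a few words in one section, or one table row, in the next amendment. Section 10.8.1.2 can stay as it is, since it only describes general management. No separate interim rule is needed, because Medical Monitor consultation already applies before such a restart.
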